4.2. Participant Dispositions

A listing and summary of study disposition for all randomized participants will be provided at the primary database lock and final database lock, respectively. Frequency counts and percentages of all participants screened, randomized, and receiving at least 1 dose of study drug will be presented by treatment groups. A listing and summary of randomized participants not receiving study drug will be provided. All participants who discontinue the study and/or study drug will be identified, and the extent of their participation in the study will be reported. If known, a reason for their discontinuation will be given. The primary reasons for discontinuation will be listed and summarized by treatment groups.

Details about the demographic and baseline characteristics, historical illnesses, and preexisting conditions, treatment compliance, concomitant medications, and important protocol deviations can be found in Appendices 1 through 5 (Section 6.1 through Section 6.5, respectively).

Analysis Type (Analysis Set)	ICE	Strategy to Handle ICE	Assumption for Missingness	Methods to Handle Missing Values at
× • /			U	Endpoints
Time-averaged Lp(a) over Day 60-180 Analysis (FAS)	None	Treatment policy	MAR	There are no ICEs. Missing values will be imputed using all nonmissing data from the same treatment arm.
Time-averaged Lp(a) over Day 30-180, Day 60-180, Day 30-360, and Day 240-360 Analysis (EAS)	"Permanent discontinuation of intervention" and initiation of excluded medications taken during the study or new initiation of Lp(a) modifying medication required to be on a stable regimen prior to treatment per protocol inclusion criteria.	Hypothetical	MAR	Data collected after the ICE will be set to missing. Missing values will be imputed using all nonmissing data (excluding data collected after ICEs) from the same treatment arm.
Lp(a), ApoB, and hsCRP MMRM (EAS)	"Permanent discontinuation of intervention" and initiation of excluded medications taken during the study or new initiation of Lp(a) modifying medication required to be on a stable regimen prior to treatment per protocol inclusion criteria.	Hypothetical	MAR	Data collected after the ICE will be set to missing. Missing values will be imputed using all nonmissing data (excluding data collected after ICEs) from the same treatment arm.

 Table EZEB.4.2.
 Strategy to Handle ICE and Missingness for Efficacy Endpoints

Analysis Type (Analysis Set)	ICE	Strategy to Handle ICE	Assumption for Missingness	Methods to Handle Missing Values at Endpoints
Lipids parameter MMRM (EAS)	"Permanent discontinuation of intervention" and initiation of excluded medications taken during the study or new initiation of Lp(a) modifying medication required to be on a stable regimen prior to treatment per protocol inclusion criteria.	Hypothetical	MAR	Data collected after the ICE will be set to missing. Missing values will be imputed using all nonmissing data (excluding data collected after ICEs) from the same treatment arm.
Lp(a) categorical analyses logistic regression (EAS)	"Permanent discontinuation of intervention" and initiation of excluded medications taken during the study or new initiation of Lp(a) modifying medication required to be on a stable regimen prior to treatment per protocol inclusion criteria.	Hypothetical	MAR	Data collected after the ICE will be set to missing. Missing values will be imputed using all nonmissing data (excluding data collected after ICEs) from the same treatment arm.

Abbreviations: ApoB = apolipoprotein B; EAS = efficacy analysis set; FAS = full analysis set; hsCRP= highsensitivity C-reactive protein; ICE = intercurrent event; Lp(a)= lipoprotein(a); MAR = missing at random; MMRM = mixed model repeated measures.

Note: For the continuous analysis of clinical laboratory tests, unscheduled measurements are excluded from analysis to reduce bias. The early discontinuation visits are considered scheduled visits.

Study	Participant Population	Baseline Observations	Postbaseline Observations
Period/Analysis			
Туре			
540 Days Study Per	iod		
1.1) Treatment-	All randomized	The baseline period is defined as	Starts after the first dose of
Emergent Adverse	participants who are	the start of screening and ends	study drug and end of the
Events (FAS)	exposed to at least 1 dose	prior to the first dose of study	study period.
	of study drug	drug (Visit 2).	
1.2) Treatment-	All randomized	Baseline will be all scheduled	Postbaseline will be defined
Emergent	participants who are	and unscheduled measurements	as above (1.1). All scheduled
Abnormal Labs	exposed to at least 1 dose	recorded during the baseline	and unscheduled
and Vital Signs	of study drug who have a	period as defined above (1.1).	measurements will be
(FAS)	normal baseline (with		included.
	respect to the direction		
	being analyzed) and a		
	postbaseline observation		
1.3) Change from	All randomized	The last scheduled nonmissing	Postbaseline will be defined
Last Baseline for	participants who are	assessment recorded prior to the	as above (1.1). Only
Labs, Vital Signs	exposed to at least 1 dose	date of first dose of study	scheduled visits will be
(FAS)	of study drug and have a	treatment during the baseline	included. The early
	baseline and at least	period defined above (1.1).	discontinuation visits are
	1 postbaseline		considered scheduled visits.
	observation		
Immunogenicity	All randomized	Baseline is defined as predose	Postbaseline will be defined
(FAS)	participants who are	collection at Visit 2.	as above (1.1). Only
	exposed to at least 1 dose		scheduled visits will be
	of study drug and have a		included. The early
	baseline and at least		discontinuation visits are
	1 postbaseline		considered scheduled visits.
	observation		

 Table EZEB.4.3.
 Baseline and Postbaseline Definitions for Safety Analyses

Abbreviation: FAS = full analysis set.

Note: For the continuous analysis of clinical laboratory tests, unscheduled measurements are excluded from analysis to reduce bias. The early discontinuation visits are considered scheduled visits.

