TSH		Х													
HbA1c		Х						Х				Х	Х	Х	
Lp(a)	Х	Х	Х	Х	Х	Х	Х	Х	Х	Х	Х	Х	Х	Х	
ApoB		Х	Χ			Х	Х	Х	Χ	Х	Х	Х	Х	Х	
hsCRP		Х	Х			Х	Х	Х	Х	Х	Х	Х	Х	Х	
HIV screening test		Х													

	Period I - Pre- Screening	Period II - Screening			Per	riod I	II T	reatm		Participants are required to fast before Visits 1-12. See Section 5.3.1. If a participant arrives not fasted, schedule the laboratory draw for another date.					
Visit number	601	1	2	3	4	5	6	7	8	9	10	11	12	ED	
Days from randomization	≤42	≤21		15	30	60	120	180	210	240	300	360	540		Visit 1 procedures may be conducted over more than 1 day if all activities are completed within the allowable visit tolerance.
Visit interval tolerance (days)	See Section 1.3	—		±3	±3	±3	±7	±7	±7	±7	±7	±7	±14		
HCV screening test		Х													If HCV antibody test is positive, it must be followed by an HCV RNA test. See Section 8.2.5.
HBV screening test		Х													If HBsAg is negative and HBcAb is positive, further testing with HBV DNA is required. If the screening HBV DNA is negative, the participant is not excluded. See Section 8.2.4.
eGFR		Х				Х		Х		Х		Х	Х	Х	Calculated using CKD-EPI method.
Postdose PK sample			x					х							 Visit 2: Collect 2 samples. 0.5 hours postdose 4-9 hours postdose (minimum 2 hours) Visit 7: Collect 1 sample. 1. 24-36 hours postdose, will require participant to return 1 day after Visit 7.
Immunogenicity (ADA)			Р	Х	Х		Х	Р		Х		Х	Х	Х	Visit 2 and 7 will be collected predose.
PK sample for immunogenicity				X	X		X	Р		x		X	X	X	Collect a time-matched PK sample for all scheduled and unscheduled immunogenicity samples. Visit 7 will be collected predose.

	Period I - Pre- Screening	Period II - Screening			Per	iod II	(I T)	reatme		Participants are required to fast before Visits 1-12. See Section 5.3.1. If a participant arrives not fasted, schedule the laboratory draw for another date.					
Visit number	601	1	2	3	4	5	6	7	8	9	10	11	12	ED	
Days from randomization	≤42	≤21		15	30	60	120	180	210	240	300	360	540		Visit 1 procedures may be conducted over more than 1 day if all activities are completed within the allowable visit tolerance.
Visit interval tolerance (days)	See Section 1.3	—		±3	±3	±3	±7	±7	±7	±7	±7	±7	±14		
Stored Samples (On dosing days, collect samples before dosing	
Optional genetics sample			X												Sample can be obtained at or after the specified visit. See Appendix 10.5.
Exploratory biomarker samples			X			X		Х		Х		Х	х		
Randomization and Dosing															

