# 8.2.7. Hypersensitivity Reactions

Many drugs, including oral agents and biologic agents, carry the risk of systemic hypersensitivity reactions. If such a reaction occurs, additional data should be provided to the sponsor in the designated CRFs.

Sites should have appropriately trained medical staff and appropriate medical equipment available when study participants are receiving study intervention. It is recommended that participants who experience a systemic hypersensitivity reaction be treated per national and international guidelines.

In the case of a suspected systemic hypersensitivity event, additional blood samples should be collected as described in Appendix 10.2.1. Laboratory results are provided to the sponsor via the central laboratory.

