# 8.8. Immunogenicity Assessments

At the visits and times specified in the SoA (Section 1.3), venous blood samples will be collected (if local regulations and ethical review boards allow) and stored for potential future analysis to determine antibody production against LY3819469. Antibodies may be further characterized for their ability to neutralize the activity of LY3819469. To interpret the results of immunogenicity, a venous blood sample will be collected at the same time points to determine the plasma concentrations of LY3819469. Samples for immunogenicity should be taken predose when applicable and possible.

In the event of drug hypersensitivity reactions (immediate or nonimmediate), additional samples will be collected as described in Section 10.2.1.

Samples will be retained for a maximum of 15 years after the last participant visit per Section 10.1.12, or for a shorter period if local regulations and ethical review boards allow, at a facility selected by the sponsor. The duration allows the sponsor to respond to future regulatory requests related to the LY3819469. Any samples remaining after 15 years will be destroyed.

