#### When to collect samples after a systemic hypersensitivity event occurs

Collect the samples listed below if a systemic hypersensitivity event is suspected. The timing should be as designated in the table, assuming the participant has been stabilized.

Obtain follow-up predose samples at the next regularly scheduled laboratory sample collection, ideally prior to the next dose after the event, to assess post-event return-to-baseline values.

Timing	Preferred Sample Type ^a	Laboratory Test ^b
Collect from 30 minutes to 4 hours	Serum	total tryptase
after the start of the event.	Serum	complements (C3, C3a, and C5a)
• Note: The optimal collection time is from 1 to 2 hours after the start of event.	Serum	cytokine panel (IL-6, IL-1 $\beta$ , IL-10 or any cytokine panel that includes these 3 cytokines)
Collect only if not already collected	Serum	LY3819469 ADA

 
on the same day as the event.
 
Note: If collecting, collect up to 12 hours after the start of the event.
 
	Serum/plasma	LY3819469 concentration

Abbreviations: ADA = anti-drug antibodies; IL = interleukin.

- ^a Sample type may be different depending on local requirements.
- ^b All samples for hypersensitivity testing will be assayed by Lilly-designated laboratory. Results will not be provided to the study site. If samples are not collected or are collected outside the specified time period, this will not be considered a protocol deviation.

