4.6. Immunogenicity

At the visits and times specified in the protocol schedule of activities (Section 1.3), venous blood samples will be collected (if local regulations and ethical review boards allow) and stored for potential future analysis to determine antibody production against LY3819469. If the data is available at the time of final database lock, the following analysis will be conducted.

Treatment-emergent antidrug antibodies (TE ADAs) are defined as those with a titer 2-fold (1 dilution) greater than the minimum required dilution if no ADAs were detected at baseline (treatment-induced ADA) or those with a 4-fold (2 dilutions) increase in titer compared to baseline if ADAs were detected at baseline (treatment-boosted ADA). A patient is evaluable for TE ADA if the patient has a nonmissing baseline ADA result, and at least 1 nonmissing postbaseline ADA result.

A listing of ADA results and TE ADA status at each visit will be provided, including ADA screening test result (detected/not detected) and the titer for detected samples.

The frequency and percentage of patients with preexisting ADA and with TE ADA will be tabulated by dose (if data warrant), where proportions are relative to the number of patients who are TE ADA evaluable. The frequency and percentage of patients with hypersensitivity and injection site reaction treatment-emergent adverse events (TEAEs) by TE ADA status will be tabulated if data warrant.

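### The scheduled-visits-only rule for ADA data leaves hypersensitivity-event samples out of TE-ADA status, so a participant positive only in such a sample is tabulated as TE-ADA negative

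*SAP*

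**What the plan says.** **Inclusion rule.** In SAP Table EZEB.4.3, the Immunogenicity row states that only "scheduled visits will be" included after baseline and treats ED visits as scheduled. Row 1.3 (change from last baseline for labs and vital signs) uses the same wording. Row 1.2 (treatment-emergent abnormal labs and vital signs) takes the opposite line: postbaseline is defined "as above (1.1). All scheduled" and, the cell continues, unscheduled measurements too. The note under the table gives the only reason for leaving unscheduled data out: "For the continuous analysis of clinical laboratory tests, unscheduled measurements are excluded from analysis to reduce bias".

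**Event samples.** Protocol 8.8 states: "In the event of drug hypersensitivity reactions (immediate or nonimmediate), additional samples will be collected as described in Section 10.2.1". Protocol 8.2.7 is softer: "additional blood samples should be collected as described in Appendix 10.2.1". Protocol 10.2.1 sets the trigger: "Collect the samples listed below if a systemic hypersensitivity event is suspected". Its table lists LY3819469 ADA, to be drawn within 12 hours of onset, but only where no ADA sample has already been taken that day. The Schedule of Activities also expects such samples: "Collect a time-matched PK sample for all scheduled and unscheduled immunogenicity samples".

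**Use of the data.** SAP 4.6 defines TE-ADA by a rise in titer. It calls a patient evaluable with a baseline result and one or more later results. It plans that "patients with hypersensitivity and injection site reaction treatment-emergent adverse events (TEAEs) by TE ADA status will be tabulated", if the data warrant it.

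**The concern.** TE-ADA status is a per-participant classification: has this person, at any time after dosing, shown a titer above the threshold? A scheduled-only rule suits means by visit, where extra samples from participants with problems would distort the average. It suits an ever-positive classification less well, because it can remove a qualifying result.

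Here the removed result is the one drawn because of the reaction, and the affected table is the one relating reactions to antibodies. A reaction with an antibody-positive sample at onset could be reported in the TE-ADA-negative column. With few reactions, one such case could change how the table reads.

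**Working it through.** The plan states no figure on this point, so the check is mainly of the text.

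**1. Where an event sample falls outside the schedule.** From the Schedule of Activities, ADA is drawn predose at Visit 2, on Days 15, 30, 120, 180 (predose), 240, 360 and 540, and at ED. Taking Visit 2 as Day 0, the gaps are:

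| Interval | Gap (days) |
|---|---|
| 0 to 15 | 15 |
| 15 to 30 | 15 |
| 30 to 120 | 90 |
| 120 to 180 | 60 |
| 180 to 240 | 60 |
| 240 to 360 | 120 |
| 360 to 540 | 180 |

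Days 60, 210 and 300 are scheduled visits without an ADA draw. On the dosing days (Visits 2 and 7) the predose draw already exists, so 10.2.1 calls for no event ADA sample. The issue therefore concerns suspected systemic reactions on other days without an ADA draw.

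**2. Whether the sample counts.** Under the Immunogenicity row it does not, unless it coincides with a scheduled or ED visit. Nothing in SAP 4.6 brings it back. The stated reason for exclusion covers continuous laboratory analyses, and TE-ADA is not one.

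**3. When the classification is wrong.** All of these must hold: the event sample was taken; it meets the TE-ADA threshold; and no scheduled or ED sample from that participant does.

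**4. How this depends on persistence (assumed values).** Suppose earlier scheduled samples were below the threshold, and each of *m* later scheduled samples meets it with probability *q*, independently. The chance that all of them miss is (1 − *q*)^*m*.

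| Later samples | *q* = 0.2 | *q* = 0.5 | *q* = 0.8 |
|---|---|---|---|
| *m* = 3 (Days 240, 360, 540) | 0.8³ = 0.512 | 0.5³ = 0.125 | 0.2³ = 0.008 |
| *m* = 1 (Day 540) | 0.80 | 0.50 | 0.20 |

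Neither *q* nor independence comes from the documents. The table shows direction only: a short-lived response can be missed, and a lasting one seldom is when several later samples remain.

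**5. Evaluability.** Take a participant whose only postbaseline ADA result is the event sample. SAP 4.6 makes this person evaluable; the table's definition of postbaseline does not. With *a* positives among *n* other evaluable participants, leaving this person out reports *a*/*n*. If the event sample was positive, the full figure is (*a* + 1)/(*n* + 1), which is higher whenever *a* < *n*. If it was negative, the full figure is *a*/(*n* + 1), which is lower whenever *a* > 0. The error can go either way.

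**6. Weight of one case (assumed count).** If 4 to 10 participants had hypersensitivity events, one reclassification would move the TE-ADA-positive share among them by 1/4 = 25 to 1/10 = 10 percentage points. The documents give no expected count. The SAP 4.6 table also counts events found by MedDRA query, a different set from the suspected systemic events that trigger sampling.

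**The case against.** The strongest defense is ascertainment. Only participants with a reaction get the extra sample, so counting it gives them an additional chance to be called TE-ADA positive and pushes the cross-tabulation toward an association. This stands as a real trade-off and is why a scheduled-only line should be kept. It is not the reason the SAP gives, and row 1.2 accepts the same trade-off for treatment-emergent laboratory abnormalities.

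Several limits also stand. Sampling is worded less firmly in Protocol 8.2.7 than in 8.8, and 10.2.1 says a missed sample is not a deviation. ADA is an exploratory endpoint, and the analysis depends on data being available at final lock. Protocol 10.2.1 also asks for follow-up samples at the next regular laboratory collection. If those include ADA, a draw on Day 60 or Day 210 would fall at a scheduled visit and might be admitted, which would shorten the gaps above.

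A reader might infer more than the text supports:

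- **That the event sample is thrown away.** It is still assayed, and 10.2.1 gives it a separate use in characterizing hypersensitivity across the program. It is excluded only from the TE-ADA derivation.
- **That the 60-day gap after the second injection measures the problem.** Reactions on the injection day have no event ADA sample to lose.
- **That the rule always lowers incidence and weakens the association.** Step 5 shows that dropping a participant can do the opposite. That case is also remote: all seven scheduled postbaseline draws and any ED draw would have to be missing, while Protocol 7.1 keeps participants who stop treatment on the visit schedule.

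**Conclusion.** The point holds in a limited form. As written, the SAP leaves an event-driven ADA sample out of TE-ADA status when the reaction falls on a day without a scheduled ADA draw. It can then place a participant who was positive only in that sample in the TE-ADA-negative column of the hypersensitivity table. This is a stated rule with that consequence, not a missing detail. The evaluability wording in SAP 4.6 and the table's scheduled-only rule also need to be reconciled.

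The size cannot be estimated from the documents. It depends on how many systemic reactions occur away from ADA draws, how often the sample is taken, and how long antibodies persist. The persistence probabilities and event counts above are illustrations. The conclusion itself rests only on reading the Immunogenicity row literally and on SAP 4.6 having no overriding provision.

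**What to change.** In the Immunogenicity row of SAP Table EZEB.4.3, replace the scheduled-only rule with wording such as: *All scheduled and unscheduled postbaseline ADA samples, including those collected under Protocol 10.2.1, are used to determine TE-ADA status and evaluability.* Add a matching sentence to SAP 4.6 so that the two agree.

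Report TE-ADA incidence and the hypersensitivity cross-tabulation from scheduled samples only as a supportive line.

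The cost is one table cell, one sentence and a programming change, with no new samples or visits. The downside is the extra chance for participants with a reaction to test positive, which the supportive line makes visible. The change can be made before final database lock, when SAP 4.6 places this analysis.

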4.3. Primary Estimand Analysis

The primary estimand (a precise definition of the treatment effect to be estimated) of interest in comparing efficacy of LY3819469 doses with placebo is the "treatment-regimen estimand" (Section 1.1). Because each patient can only take 1 dose for the first 6 months, there are no ICEs of treatment discontinuation. The primary efficacy assessment, guided by the "treatment regimen estimand", will be conducted using the FAS.

4.3.1. **Definition of Endpoint(s)**

The primary efficacy measure will be based on the contrast between each treatment group of LY3819469 and placebo for the percent change from baseline in time-averaged Lp(a) over Days 60 to 180 in participants with elevated Lp(a). The Lp(a) over Days 60 to 180 is defined as AUC between Day 60 to Day 180 divided by 120.

4.3.2. Main Analytical Approach

Percent change from baseline in time-averaged Lp(a) over Days 60 to 180 will be analyzed using MMRM modeling strategy for the treatment regimen estimand as detailed in Section 4.1. For the primary analysis (up to Day 180), the 2 LY3819469 treatment groups assigned to 400 mg will be pooled into 1 treatment group because participants are receiving the same study intervention in the first 180 days. Patients without any postbaseline measurement will be excluded from this analysis.

Comparisons of difference in time-averaged response from baseline for treatment group k versus placebo reference group, indexed by R, will be made by using contrasts of LS means to calculate

$$\hat{\theta}_{\Delta k} = \sum_{t} w_t \left(\hat{\beta}_{k:t} - \hat{\beta}_{R:t} \right),$$

where $\hat{\beta}_{k:t}$ corresponds to the LS mean of treatment group k at time t, R represents the placebo reference group, and w_t is the weight at time t informed by the trapezoidal rule. Estimates and CIs will be constructed from the model-based versions using the delta method.

Mean (SD) percent change over time in fasting Lp(a) will be plotted by LY3819469 treatment group and pooled placebo group, until there are fewer than 10% of the FAS population at a given visit. Waterfall plots of by-patient percent changes from baseline to Days 30, 60, 180, 360, and 540 time point will also be provided.

